**10.1 DEFINITIONS OF AE, SAE, SADE, USADE**

Adverse Event	Any untoward medical occurrence in a subject who has been treated with the device that does not necessarily have causal relationship with the treatment.
Adverse Device Effect	Any unfavorable and unintended sign (including an abnormal laboratory finding), symptom, or disease that is possibly related to the study device.
Serious Adverse Event (SAE)	Any untoward medical occurrence that: 
 
• Results in death
 
• Is life-threatening
 
• Requires in-patient hospitalization or prolongs existing hospitalization
 
• Necessitates medical or surgical intervention to preclude permanent impairment of a body function or permanent damage to a body structure
 
• Sight threatening
 

Unanticipated Adverse Device Effect	Any serious adverse effect on health or safety, any life-threatening problem or death caused by, or associated with a device if that effect, problem, or death was not previously identified in nature, severity, or degree of incidence in the clinical investigational plan; or any other serious problem associated with a device that relates to the rights, safety, or welfare of subjects (21 CFR 812.3(s)). Any sight-threatening event, whether listed in the protocol or not, is considered to be reportable as a UADE

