# **10 ADVERSE EVENTS (AES)**

Adverse Events are defined below. Adverse events that occur in the eye during the trial, whether considered to be device related or not, must be documented in the subject’s records. Non-ocular adverse events do not need to be recorded as adverse events unless they meet the definition of serious adverse event or are believed to be related to the study device or a study procedure. Date of the event, its severity, treatment (if any), and the assessed relationship of the event to the study device will be recorded on the Adverse Event Form. Conditions which exist at the time the subject is enrolled will be considered pre-existing conditions and do not need to be recorded as adverse events unless they increase in severity during the study.

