### 10.3 REPORTING ADVERSE EVENTS AND UNANTICIPATED ADVERSE DEVICE EFFECTS

Identification, collection, and reporting of adverse event information is the responsibility of the principal investigator or designated investigator. The investigator records the date of the event, its severity, treatment (if any) and the assessed relationship of the event to the study device on the Adverse Event Case Report Form (AE CRF).

Any ocular-related **serious adverse event (SAE)** should be reported to the study sponsor within one working day of learning of the event. Non-ocular-related SAEs should be reported to the study sponsor within two working days of learning of the event. Record all applicable information in the source document, enter into the EDC system and email the AE CRF to [[contact]](mailto:[contact]).

Any **unanticipated adverse device effects (UADE)** must be reported to the following two entities:

1. The study sponsor – Within one working day of the investigator first learning of the event, record all applicable information in the source document, enter into the EDC system and e-mail the AE CRF to [[contact]](mailto:[contact]); and
2. The reviewing IRB – As soon as possible, but no later than 10 working days after the investigator first learns of the event, report per the IRB's instructions.

The sponsor will conduct an evaluation of unanticipated adverse device effects. If the sponsor determines that an unanticipated adverse device effect presents an unreasonable risk to subjects, parts of the investigation presenting risks will be terminated. Termination will occur no later than 5 working days after the sponsor makes such a determination and no later than 15 working days after the sponsor first received notice of the effect.

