### **12.6.4 SAFETY ANALYSIS**

All adverse events will be reported by study group and AE category. Any serious adverse events will be completely described in the study report. The primary safety endpoint will be summarized for each study group.

We will compute the incidence of ocular events in two ways: first as a simple proportion, counting the number of subjects with any event (that is, counting the first event per person in either eye), then as an incidence rate, counting all events including repeated events per subject.

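### The SAE definition covers intervention to prevent permanent damage but not permanent damage itself, so some lasting injuries can be classed as non-serious

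*Combined protocol and SAP*

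**What the plan says.** Protocol Section 10.1 defines an SAE by five alternatives:

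1. "Results in death"
2. "Is life-threatening"
3. "Requires in-patient hospitalization or prolongs existing hospitalization"
4. "Necessitates medical or surgical intervention to preclude permanent impairment of a body function or permanent damage to a body structure"
5. "Sight threatening"

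Three other rules depend on whether an event is serious.

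- **Recording.** Section 10 requires every ocular event to be documented, related or not. For the rest it says "Non-ocular adverse events do not need to be recorded as adverse events unless they meet the definition of serious adverse event", with one further exception for events believed related to the device or a study procedure.
- **Sponsor notice.** Section 10.3 gives ocular SAEs one working day. For the others, "Non-ocular-related SAEs should be reported to the study sponsor within two working days of learning of the event". It states no deadline for a non-serious AE.
- **Reporting.** Section 12.6.4, repeated in SAP Section 22.6, says "Any serious adverse events will be completely described in the study report". It makes no such promise for other AEs.

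Sections 10.1 and 10.3 also set up a separate UADE route. It has its own one-working-day notice to the sponsor and a report to the IRB within 10 working days.

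**The concern.** Criterion 4 makes an event serious when intervention was needed to avert permanent damage. No criterion makes an event serious because permanent damage occurred. An averted injury can therefore rank above one that left a lasting deficit. The documents give no reason for this, and it reads as an omission.

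The gap is relevant to this device. Section 11.5 names eyelid overheating as the first major risk, and Section 10.2 lists lid burn and pressure-induced lid injury among the anticipated events. A lid scar or deformity can be permanent without hospitalization or any threat to sight. At stake are the prompt notice to the sponsor, the SAE label and the full description in the report. For unrelated non-ocular events, the record itself is at stake.

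**Working it through.** The documents state no figure for this point. The check traces two cases through the rules and then sizes the exposure.

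**Case A: a permanent lid injury with no hospitalization, no threat to sight and no intervention needed to prevent the damage.** Examples are damage found late, damage that cannot be treated, or damage managed by observation.

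| Rule | Result |
|---|---|
| Five SAE criteria (10.1) | 0 of 5 met |
| SAE notice (10.3) | Not triggered |
| Full description (12.6.4, SAP 22.6) | Not required |
| Recording (10) | Required, as an ocular AE |
| Tabulation by group (12.6.1, 12.6.4) | Yes |
| UADE route (10.1, 10.3) | Possible but uncertain |

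The UADE route is uncertain for two reasons. For an event that is not fatal, life-threatening or sight-threatening, the UADE text requires a serious effect or problem, and the protocol defines serious only through the same five criteria. Also, lid burn and pressure injury are already listed as anticipated in Section 10.2. An investigator could argue that the severity was not foreseen, since that list gives no grades and does not mention scarring. Two sites could reasonably decide differently. In addition, this part of the UADE text concerns device-associated effects, so it offers nothing for a permanent injury under Restasis before crossover.

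**Case B: a disabling non-ocular event managed as an outpatient, not life-threatening, with no preventive intervention needed, and judged unrelated.** It meets 0 of the 5 criteria and neither exception in Section 10, so it need not be recorded. Section 6.2, however, says in a parenthesis that all adverse events will be recorded. The two sections do not agree.

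**Exposure.** The inputs are up to 175 subjects per group (Sections 9.3 and 12.7), two scheduled TearCare procedures in the TearCare group and one at crossover in the Restasis group (Section 7.1).

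- Full enrollment with no dropout, before conditional retreatment: 2 × 175 + 1 × 175 = 525 procedures.
- With the 10% to 11% loss per six months in Section 12.7, assumed to have occurred by Month 5:
  - 10%: 175 × 0.90 = 157.5 per group, so 175 + 2 × 157.5 = 490.
  - 11%: 175 × 0.89 ≈ 156 per group, so 175 + 2 × 156 = 487.

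These are procedures, not events. The documents give no rate of permanent lid injury, and none of the four prior studies summarized in Section 5.2 reports one.

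**The case against.** The strongest reply is that the practical loss is small, and much of that reply stands.

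- **Criterion 4 is wider than it first looks.** It asks whether intervention was necessary, not whether it succeeded. A burn treated to prevent scarring that scarred anyway is an SAE. The gap is confined to injuries for which no such intervention was needed.
- **The UADE route may catch a scarring device injury**, with the same one-working-day notice and an IRB report. This stands as a possibility only, for the reasons given in the working.
- **Ocular events are not lost.** They are documented with severity, treatment and relationship. Procedure- or treatment-related AEs are the primary safety endpoint (Section 12.6.2), and all AEs are tabulated by group. No hypothesis test depends on the SAE count, and the documents state no stopping boundary based on it.

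A reader might infer that any scarring lid injury escapes expedited reporting. The documents do not support that, because criteria 3, 4 and 5 and the UADE route can each bring it in. A reader might also infer that a disabling non-ocular event leaves no record. Section 10 removes the duty to record it only if it is non-serious and judged unrelated. It does not forbid recording, and Section 6.2 points the other way. Nor do the documents show that the SAE count is too low, since that depends on such an event occurring.

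What the reply does not remove is that the list is closed, nothing elsewhere adds the missing outcome, and a site following it exactly would class some permanent injuries as non-serious.

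**Conclusion.** The omission is real and its consequences are narrow. Followed as written, the definition lets a permanent lid injury of the Case A kind miss the SAE label, the SAE notice and full description, unless it is judged a UADE. It also leaves an event of the Case B kind outside the duty to record in Section 10, in conflict with Section 6.2.

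No frequency can be derived from the documents. The events should be rare, and 525 scheduled procedures is a full-enrollment figure without dropout, not a minimum. The SAE count by group could be too low only if such events occur. No efficacy result, power or type I error figure is affected. The conclusion rests on sites applying the five criteria as an exhaustive list, which is how Section 10.1 presents them. Correction is worth making because it is cheap and bears on the first-named device risk.

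**What to change.** 1. Add a sixth SAE criterion to Section 10.1 for events that result in permanent functional impairment or permanent structural damage, in the same terms as the existing fourth criterion. Keep the fourth criterion.
2. Reconcile Sections 6.2 and 10 so that one rule states which adverse events are recorded, and align the AE form guidance with it.
3. Review recorded AEs and re-classify any with permanent sequelae under the amended definition.

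The text change is small, and the SAE count may rise slightly. The look-back may cost more than a database query: the AE fields named in Sections 10 and 10.3 are date, severity, treatment and relationship, and outcome is not among them, so source records may have to be read. It cannot recover non-ocular events that were never recorded, which is a reason to make the change early.

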**10.2 LIST OF ANTICIPATED POTENTIAL OCULAR ADVERSE EVENTS**

Anticipated potential adverse events include those that might reasonably be expected to occur in this study because they are associated with dry eye disease, the risk analysis for TearCare System or study testing methods. Please refer to Restasis label for potential AEs related to Restasis use.

- Eyelid/eye pain requiring discontinuation of the study procedure
- Eyelid/eye pain requiring treatment  $\geq 1$  day after the study procedure
- Eyelid irritation, or inflammation
- Discomfort or pain of eyelids or orbit
- Ocular symptoms (such as burning, redness, tearing, visual disturbance, redness)
- Burn, erythema, or swelling of the eyelids
- Thermal injury to the eye, including conjunctiva, cornea or lens
- Allergic or inflammatory reaction to medical adhesive on the SmartLid device

- Physical pressure-induced injury to the eyelid
- Corneal deformation
- Foreign body sensation
- Formation of a chalazion or stye
- Infection of the eyelid or ocular surface
- Ocular surface irritation or inflammation (e.g., Conjunctival injection, conjunctival or corneal abrasion, chemosis)
- Allergic or inflammatory reaction to the SmartLid
- Worsening of dry eye symptoms
- Loss in BCVA (ETDRS) of  $\geq 10$  letters

### 10.3 REPORTING ADVERSE EVENTS AND UNANTICIPATED ADVERSE DEVICE EFFECTS

Identification, collection, and reporting of adverse event information is the responsibility of the principal investigator or designated investigator. The investigator records the date of the event, its severity, treatment (if any) and the assessed relationship of the event to the study device on the Adverse Event Case Report Form (AE CRF).

Any ocular-related **serious adverse event (SAE)** should be reported to the study sponsor within one working day of learning of the event. Non-ocular-related SAEs should be reported to the study sponsor within two working days of learning of the event. Record all applicable information in the source document, enter into the EDC system and email the AE CRF to [[contact]](mailto:[contact]).

Any **unanticipated adverse device effects (UADE)** must be reported to the following two entities:

1. The study sponsor – Within one working day of the investigator first learning of the event, record all applicable information in the source document, enter into the EDC system and e-mail the AE CRF to [[contact]](mailto:[contact]); and
2. The reviewing IRB – As soon as possible, but no later than 10 working days after the investigator first learns of the event, report per the IRB's instructions.

The sponsor will conduct an evaluation of unanticipated adverse device effects. If the sponsor determines that an unanticipated adverse device effect presents an unreasonable risk to subjects, parts of the investigation presenting risks will be terminated. Termination will occur no later than 5 working days after the sponsor makes such a determination and no later than 15 working days after the sponsor first received notice of the effect.

## 11 RISK-BENEFIT ANALYSIS

### 11.1 ANTICIPATED CLINICAL BENEFITS

The TearCare® procedure will be performed with the aim of reducing the signs and symptoms of dry eye.

### 11.2 ANTICIPATED ADVERSE DEVICE EFFECTS

Anticipated adverse effects associated with the TearCare System have been described above in Section 10.2.

### 11.3 RISKS ASSOCIATED WITH PARTICIPATION IN THE CLINICAL INVESTIGATION

All anticipated study risks are listed in Section 10.2.

### 11.4 POSSIBLE INTERACTIONS WITH CONCOMITANT MEDICAL TREATMENTS

It is anticipated that there will be no interactions with concomitant medical treatments.

### 11.5 STEPS THAT WILL BE TAKEN TO CONTROL OR MITIGATE THE RISKS

The major risks to the subjects and the steps taken to control or mitigate them are described below:

1. Overheating of the eyelids: All TearCare procedures will be done in the investigator's office under direct supervision of the investigator. During TearCare procedures in this study heat will be applied to the eyelids at a temperature ranging from 41-45°C. This temperature range was selected based on research. The investigator can adjust the temperature up or down to a level that is comfortable for the subject, and may also shut off the System at any time if it is too uncomfortable or painful. In addition, the TearCare System is designed to monitor and regulate the temperature at the tissue-contacting

 Medical electrical equipment Part 1: General requirements for basic safety and essential performance (IEC 60601-1).

surface of the SmartLid devices and not to exceed the maximum allowable temperature.

2. **Corneal abrasion:** If the SmartLid devices are not positioned properly or come loose during the procedure, there is the potential for a corneal abrasion. To mitigate this, the investigator will apply the strips to the subject and will monitor their position during the procedure to ensure they remain in place and secure.

In addition, there is the possibility of corneal abrasion or abrasion of the eyelid surface during expression of the meibomian glands. To reduce the chance of abrasion, the forceps have been designed with smooth surfaces (i.e., no rough edges) and investigators will be trained on how to perform expression according to this protocol.

In addition to the above, the following mitigation steps have also been taken to reduce the risks in this study:

- The device has been tested to demonstrate that it meets performance and safety specifications, as described in Section 5.1.
- Instructions for Use on how to use TearCare in this study will be provided to each investigator.
- Investigators will be trained in how to correctly apply and remove the SmartLid devices and operate the TearCare System.
- Investigators will be trained in how to perform lid debridement and meibomian gland expression using the TearCare Clearance Assistant as described in this protocol.
- The study staff will be trained to perform procedures required in this protocol.

## 12 STATISTICAL CONSIDERATIONS

### 12.1 EVALUABILITY

All subjects on whom the TearCare or Restasis is attempted will be considered evaluable for the safety analysis. All eyes that have at least one follow-up visit and have no major protocol deviations will be evaluable for the per protocol analysis.

### 12.2 ANALYSIS POPULATIONS

- Intent-to-Treat Population - The intent-to-treat (ITT) population includes all randomized subjects. The primary and secondary efficacy analyses will be performed on the ITT population. Subjects will be analyzed as randomized.

- Per Protocol Population – The per protocol (PP) population includes all subjects who have at least one follow-up visit and have no major protocol deviations, including specifically no use of dry-eye medications (Doxycycline, Xiidra). Subjects will be analyzed as treated.
- Safety Population – The safety population will include all subjects on whom the TearCare or Restasis is attempted. The safety population will be analyzed for all safety assessments. Subjects will be analyzed as treated.

## 12.3 SUBJECT ACCOUNTABILITY

A complete accounting of subjects by visit will be provided, including reasons for dropout, if known.

## 12.4 DEMOGRAPHICS AND BASELINE CHARACTERISTICS

Demographic variables gender, race, ethnicity, and age will be summarized for all enrolled subjects, along with medical history. Descriptive statistical summaries of pre-treatment parameters (min, max, median, mean, standard deviation) will also be provided for each group. This includes baseline measurements for each of the study endpoints: TBUT, Total Meibomian Gland Secretion Score, Number of Meibomian glands with any/clear liquid, Corneal Staining, Conjunctival Staining, Blink Rate, Schirmer Score, OSDI Score, SANDE Score, and Eye Dryness Score.

## 12.5 EFFECTIVENESS ENDPOINTS AND ANALYSIS METHODS

All primary and secondary endpoints will be evaluated at 6 months. Outcomes measured on a per-eye basis will be analyzed using data from both eyes, with linear mixed effect models to account for within-person correlation (correlation between right and left eyes) as described in Appendix B.

### 12.5.1 DESCRIPTIVE ANALYSES

The quantitative variables will be summarized using number of subjects (n), mean, median, standard deviation, minimum and maximum. The qualitative variables will be summarized using counts and percentages.

Summaries of all endpoints will be presented by treatment group and visit. Summaries will also be provided for demographics, baseline medical history, concurrent therapies, and subject disposition.

### 12.5.2 PRIMARY EFFECTIVENESS ENDPOINTS

The primary effectiveness endpoints are:

- the change from baseline in Tear Break-Up Time (TBUT) at 6 months
- the change from baseline in total OSDI at 6 months

The primary endpoint of the change from baseline in Tear Break-Up Time (TBUT) at 6 months will be analyzed using linear mixed effects (LME) models adjusting for baseline and site, and with a random subject effect. These will allow for the proper incorporation of within-person correlation into the statistical models and will also allow for adjustment for baseline measurements.

Details of the LME models are provided in the Statistical Analysis Plan (SAP) provided in Appendix B. Hypotheses regarding the primary and secondary effectiveness outcomes are described below.

The primary endpoint of the change from baseline in total OSDI at 6 months will be analyzed using ANCOVA models adjusting for baseline and site.

### **12.5.3 PRIMARY EFFECTIVENESS HYPOTHESES**

The primary study hypotheses regard the superiority of the TearCare treatment as compared to Restasis, for Tear Break-Up Time (TBUT) and total OSDI. The primary endpoints will be tested for TearCare in a hierarchical fixed sequence. The statistical hypotheses are stated in terms of one-sided hypotheses, although statistical testing will be two-sided.

To demonstrate superiority of the TearCare treatment to the Restasis control for TBUT we will test the following hypotheses:

$H_{01}$ : There is no difference between TearCare and Restasis in the mean change from baseline in TBUT at 6 Months.

$H_{11}$ : The mean change from baseline in TBUT at 6 Months is greater with TearCare than with Restasis.

If  $H_{01}$  is rejected, then the study will be considered a success and we will test the following hypotheses to further evaluate superiority of the TearCare treatment to the Restasis control for total OSDI:

$H_{02}$ : There is no difference between TearCare and Restasis in the mean change from baseline in total OSDI at 6 Months.

$H_{12}$ : The mean change from baseline in total OSDI at 6 Months is less with TearCare than with Restasis.

### 12.5.4 POOLABILITY

Using a linear mixed effects modeling approach described in Appendix B, poolability of the effectiveness outcomes will be evaluated across centers by testing a Treatment-by-Center interaction (TxC). If the TxC interaction is significant at  $\alpha=0.15$ , a Center effect will be included in the final model and results will be reported separately by Center. For this analysis, Centers with less than 5 enrolled subjects will be combined into a single, virtual center.

### 12.5.5 MISSING DATA

No missing data imputation will be carried out beyond what is built-in to the mixed-effects modeling approach to be used in the primary effectiveness analysis.

No secondary effectiveness endpoints or safety endpoints will be imputed.

